13.9.3 Exploratory outcomes

Intervention effects on HIV testing and diagnosis at ICCs

We will assess whether the intervention, when compared with the control condition, is associated with off-target effects at ICCs. We hypothesize that treatment incentives for HIV-positive clients may also attract more people to the ICC for HIV testing, and subsequently, lead to more newly diagnosed HIV-positive persons. We will use a similar two-stage procedure as described above to calculate the mean pair-wise differences in rates.

Analysis plan for mixed methods evaluation of HIV care incentives

The mixed methods evaluation will include a quantitative and qualitative component. The quantitative component comprises close-ended questions about perceptions of and experiences with incentives that will be included in the questionnaire for the final (24-month) study visit at the 8 incentive sites. These data will be summarized to quantify overall and site-level variability in perceptions about treatment incentives.

Qualitative data will be obtained by in-depth interviews as described. Transcribed interviews will be translated from the local language and entered into Atlas.ti, a free-text organizing program and analyzed using content analysis. We will identify core consistencies and meanings in the data through careful repeated reading of interview texts. Coding involves labeling sections of

text based on themes and particular domains of interest related to the study aims. We will use an “open coding” procedure whereby the beginning phases of data analysis will involve an inductive approach to elucidate patterns and themes in the data to generate codes for analysis. New themes can be generated from the analysis in addition to those established a priori. Early coding will be followed by a more deductive process whereby relevant text from the remaining interviews is coded using Atlas.ti within the framework established early on. The outputs of the coded text will then be reviewed for similarities and differences and synthesized using matrices structured by the main themes of the analysis. Quotes representing each theme will be reviewed again within the context of the full text of the interview to contextualize and confirm interpretation. Results will be summarized/presented by main themes. We will focus on codes/themes related to barriers to using the ICCs, perceived quality, and perceptions about incentives.

Analysis plan for community-level effects assessed by RDS surveys

Inferences about the effect of HIV care incentives on community-level outcomes will be based on study arm differences in outcomes measured at the evaluation RDS survey, adjusted for values of outcomes at the baseline survey (which was done in 2016/2017). Because RDS participants are recruited without respect to whether they have accessed services at ICCs, they can provide an unbiased estimate of community-level impact.

The primary community-level outcome will be viral suppression among HIV-positive individuals in the RDS sample. Using the same approach as the primary outcome analysis, we will calculate the difference in the RDS II weighted proportions within each matched pair and then calculate the unweighted mean of the pair-wise differences with a 95% confidence interval. Comparisons will use RDS-weighted proportions, which will be calculated using the RDS-II estimator (7), which accounts for the self-reported network size of each individual in the analysis. With these weights, RDS can provide inferences about the prevalence of viral suppression (and other outcomes) in the underlying population. RDS weighting is subject to assumptions, some of which cannot be validated, therefore we will also compare the unweighted prevalence estimates. A paired t-test will test the hypothesis that the observed pair-wise difference is statistically different from zero. Adjustment for baseline viral suppression at the baseline survey as a cluster-level factor will be conducted using the two-stage approach as described in the primary analysis. Similar analytic methods will be applied to secondary outcomes that are proportions including recent HIV testing, awareness of HIV status, HIV care, current ART use, and prevalence of viremic individuals in the community, as well as the HIV incidence rate (unweighted only).

As a sensitivity analysis, we will adjust for demographic factors as confounders (age, sex, marital status, educational attainment) using the two-stage procedure if the factor has a large (odds ratio >2 or <0.5) and statistically significant ($p<0.05$) association with the intervention status and the outcome. Additional sensitivity analyses will consider other approaches including an analysis of the within-cluster difference in outcome prevalence between serial cross-sectional studies (baseline RDS and evaluation RDS after 24 months of intervention) and individual-level models. These models include fixed effects (e.g., matched pair effect), random effects (e.g., clusters), scaled RDS weights as sampling weights, and allow adjustment for baseline covariates at the individual and cluster level. Additionally, we will conduct pre-specified analyses that are stratified by key population (PWID and MSM).

Analysis plan for cost-effectiveness

We will conduct 2 cost-effectiveness analyses from 3 perspectives (patient out-of-pocket costs, health care payer (governmental), and societal, combining patient and payer costs). The first analysis will compare the cost-effectiveness of HIV care incentives versus the control condition using the primary and secondary outcome measures to yield, for example, the cost per additional individual surviving with viral suppression at 24 months. Using the same approach, we will also explore cost-effectiveness with respect to secondary outcomes including newly identified HIV-infected persons and HIV incidence.

1. Costing: We will apply standard micro-costing methods from the US Task Force on Cost-effectiveness Analysis to assess care and intervention costs. The intervention costs will be based on fair market value of the non-cash incentives. For individuals, we will focus on the following major and readily captured medical and productivity measures: hospitalizations, physician and non-physician outpatient visits, medications, productivity (full-time, part-time work), out of pocket medical costs, and time and wages lost due to medical appointments including travel. We will adhere to recommendations for trial-based economic data collection (e.g., identifying resource measures, data collection, baseline cost, pilot testing, validation, patient-level costing, national costing and standard reporting). We will consult policymakers for the most relevant outcomes of interest to them and for their preferred sources of national resource unit costs, e.g., based on India's National Pharmaceuticals Pricing Policy and National Health Accounts of India.
2. Effectiveness: The initial cost-effectiveness analysis will combine the costing analysis from 3 perspectives (patient, payer and societal) for the 24-month intervention period with the primary and secondary outcomes of the cluster-randomized trial using statistical analyses delineated above. A second cost-effectiveness analysis will extend the end of trial results to a lifetime time horizon. Because induced benefits or costs may extend beyond the time horizon of the study (e.g., mortality benefit from viral suppression), we will project the future implications on health and on costs using computer simulation models. Markov or Monte Carlo simulation models track hypothetical cohort members as some individuals develop HIV or as those with HIV infection have stable, improved, or worsened health status or die. The computer simulations track the proportion of the cohort that is alive each year until all cohort members have died or the desired analytic time horizon has been reached. Consistent with WHO recommendations, we will obtain quality of life estimates as disability-adjusted life years (DALYs).

Economic model development will include the following steps: (1) systematic literature search to identify existing data to estimate model parameters and previously published economic models, (2) data synthesis to estimate means and ranges of uncertainty, (3) Markov and Monte Carlo simulation model development based on the primary study and literature data. Search strategies will include those recommended by Health Technology Assessment, supplemented by hand-searching of bibliographies and consultation with experts. Data synthesis will apply standard quantitative pooling methods typically used in meta-analysis (such as a random effects model) when sample sizes are available. When sample size is not available, means or medians of published data will be applied with ranges specified in the

literature. The Markov model construction will use standard decision analysis software (Decision Maker, DATA by Treeage or equivalent). Because costs are discounted to reflect time preferences (money spent now is more valuable than money spent one year from now), life expectancy will also be discounted in accordance with cost-effectiveness recommendations. Model validation or calibration to external data (comparison and adjustment, if necessary, of predicted to observed outcomes) will be performed.

3. Cost-effectiveness analyses: By extending the time horizon for the analysis and by translating trial outcomes into DALYs, the cost-effectiveness analysis becomes a cost-utility analysis where the outcome is expressed as the incremental cost-effectiveness ratio (ICER) per disability-adjusted life-year gained. We will compare of the ICER for the incentive intervention with the ICERs of other well-accepted medical interventions. Based on WHO criteria, the intervention will be considered “highly cost-effective” if the ICER falls below the per capita GDP of the country (~\$1500 for India) and “cost-effective” if the ICER falls below 3 times the per capita GDP.

Extensive sensitivity analyses will be performed, varying each variable or groups of variables over their plausible ranges to determine their impact on the cost-effectiveness of HIV care incentives versus the control condition. The translation of the Markov model into a Monte Carlo simulation will involve assigning distribution functions for each parameter and determining the range of plausible values to capture their uncertainty, and re-evaluating the computer simulations with boot strap samples. This will be used to determine cost-effectiveness acceptability curves, which incorporate all of the uncertainty to estimate the likelihood that the intervention will have an ICER that makes it cost-effective or cost-saving.

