13.4 Sample Size Considerations

We calculated power for comparing the primary endpoint within matched cluster pairs, *survival with suppressed viral load, defined as HIV RNA <150 copies/mL in plasma or serum, at 24 months*, among the cohorts of HIV-positive study participants. Cluster-randomized designs require consideration of the between-cluster coefficient of variation (k), a measure of variation between clusters. In general, the more variability in outcome between clusters, the larger the sample size required to detect a given difference. The coefficient of variation in a matched study needs to take into account the matching correlation (k_m), in other words how much of a reduction in pair variability is accomplished by matching. More successful matching is associated with lower k_m values. We calculated the k_m using baseline RDS data from a prior trial for a hypothetical set of matched pairs based on the proposed matching criteria for this trial as described above. The values of k_m ranged from 0.08 to 0.15 when considering RDS-II weighted and unweighted estimates of the outcome of interest. In addition to consideration of k_m , we also considered other factors specified by the sample size formula from Hayes et al. (6):

$$c = 2 + (Z_{\alpha/2} + Z_{\beta})^2 [\pi_0(1 - \pi_0)/n + \pi_1(1 - \pi_1)/n + k_m^2(\pi_0^2 + \pi_1^2)](\pi_0 - \pi_1)^2$$

where π_0 and π_1 are the true population proportions in the absence and presence of the intervention, respectively, n is the number of individuals within each cluster, $Z_{\alpha/2}$ and Z_{β} are the standard normal distribution values corresponding to the upper tail probabilities of $\alpha/2$ and β , respectively and k_m is the coefficient of variation within matched pairs.

Within our calculations, we varied the k_m from 0.10-0.20 based on our preliminary data, the sample size per cluster from 50-150 to account for varying levels of loss to follow-up, and the outcome prevalence in control condition clusters from 25-45%. The number of cluster pairs needed was relatively insensitive to the prevalence of outcome in the control group and the cluster size as long as the sample size was >70 per cluster.

Figure 2 shows the number of cluster pairs needed (y-axis) to provide 80% power to detect differences of 0.05 to 0.30 (x-axis) across a range of k_m values (different colored lines) assuming a sample size of 150 per cluster, two-sided alpha=0.05, and 25% outcome prevalence in the

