control clusters. With 8 cluster pairs, we will have 80% power to detect differences of 8 percentage points (risk ratio = 1.32) if the k_m is 0.10, and 10 percentage points (risk ratio = 1.4) if the k_m is 0.15. If the prevalence in control clusters is 40% then the detectable difference is 10 percentage points (risk ratio = 1.4) if the k_m is 0.10.

[figure not shown]

Figure 2. Number of matched pairs needed to detect differences. Red dotted line indicates 8 pairs of clusters

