13.6 Randomization and Masking Procedures

In cluster-randomized trials with a relatively low number of sites (clusters), substantial imbalances between study arms can emerge easily by chance. To reduce the likelihood of large study arm imbalances for key variables, we restricted the pool of potential allocation combinations by removing combinations with large baseline imbalances. With no restrictions, there were a total of 16 potential allocations (i.e., 4^2) within each stratum (PWID/MSM), or 256 overall allocations. First, to reduce large imbalances within the strata, randomization allocations were dropped ($n=8$, 4 in each stratum) due to imbalances in prevalence of viremic persons or viral suppression (i.e., all sites with higher/lower prevalence were allocated to one arm). This resulted in 12 allocations for each stratum. These allocations crossed (PWID x MSM), resulted in 144 potential allocations (i.e., 12^2). Then, an additional overall restriction was placed in which allocations were dropped ($n=36$) due to imbalances in prevalence of viremic persons or viral suppression (i.e., higher/lower prevalence 6:2 pair ratio in different arms). This resulted in a total of 108 potential allocations. We checked across all these potential allocations for sites that either always or never appeared in the same study arm. No sites always or never appeared in the same

arm - with the exception matched sites, which, by definition, never appeared in the same arm.

Of the 108 allocation combinations that remained after site pairing and restriction, one allocation was selected in a ball drawing ceremony on January 3, 2018 that was refereed by two statisticians who were independent of the study. The ceremony was video recorded and is available at <https://youtu.be/UmXBG2CluNA>. Because of the cluster randomized design, masking participants or research staff was not feasible. However, the randomization team withheld the randomization results for each site pair until cohort recruitment was complete or nearly complete at both sites in the pair. The implementation teams in India recruited cohorts at each site without knowing whether the site would be intervention or control.

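### The adjusted RDS comparison fits a site-level covariate but keeps an ordinary paired t-test on 8 pairs, so its confidence intervals are somewhat too narrow

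*Combined protocol and SAP*

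**What the plan says.** Section 13.9.3 (community-level effects) bases inference on arm differences at the evaluation survey, adjusted for the 2016/2017 baseline survey. It first describes RDS-II weighted differences within each pair and their unweighted mean, then the test: "A paired t-test will test the hypothesis that the observed pair-wise difference is statistically different from zero". Adjustment follows: "Adjustment for baseline viral suppression at the baseline survey as a cluster-level factor will be conducted using the two-stage approach", with a reference back to the primary analysis. Similar methods are to be used for the other RDS outcomes, and analyses stratified by key population are pre-specified.

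The two-stage method is set out in section 13.9.1. A logistic model with a term for each pair and baseline suppression, leaving out the intervention, gives expected events per site. Observed and expected are compared within pairs, and a paired t-test is applied. There the covariate is each participant's own baseline suppression.

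Section 13.6 describes randomisation restricted on viral suppression and prevalence of viremia: "This resulted in a total of 108 potential allocations".

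No section states degrees of freedom for the adjusted RDS test or a small-sample correction for a site-level covariate.

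**The concern.** In the cohort analysis the covariate varies between participants within a site, so estimating its slope uses essentially none of the between-site information. In the RDS analysis it is constant within a site. Once pair terms are fitted, the only information about its slope is how the 8 within-pair outcome differences move with the 8 within-pair baseline differences. Fitting that slope shrinks the residual differences, and a paired t-test then treats them as 8 free observations with 7 df.

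There is a second effect. The first stage ignores arm, so when the covariate is not perfectly balanced it absorbs part of any true intervention effect. The estimate is pulled towards zero and the interval is centred in the wrong place.

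The adjusted comparison is the lead community-level analysis, so its interval is the one that will be reported.

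**Working it through.** **Inputs.** 8 pairs and two-sided alpha 0.05 (13.4); 108 allowed allocations (13.6); site-level covariate and paired t-test (13.9.3, 13.9.1).

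**The plan's own figures.** With c = 2 + (1.960 + 0.842)² × V / (π0 − π1)² and V = π0(1−π0)/n + π1(1−π1)/n + k_m²(π0² + π1²), n = 150:
- 25% v 33%, k_m 0.10: V = 0.00125 + 0.00147 + 0.00171 = 0.00444, c = 7.44, so 8 pairs. This agrees with "With 8 cluster pairs, we will have 80% power to detect differences of 8 percentage points".
- 25% v 35%, k_m 0.15: c = 7.44. 40% v 50%, k_m 0.10: c = 7.78. Both round up to 8.

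In the first case the SD of a pair difference is √0.00444 = 0.067. An effect of one SD is then about 7 points, close to the effect the trial was sized for. This is only a guide, because the number of HIV-positive RDS participants per site is not given.

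**Allocation counts.** 12 per stratum, 12² = 144, then 108 are reproduced if the suppression and viremia orderings differ in one pair per stratum (an assumption).

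**Algebra.** Let D be the 8 outcome differences (intervention minus control), x the baseline differences and τ the effect, with D = τ + βx + e.
- First-stage slope, ignoring arm: b = ΣDx / Σx².
- Two-stage estimate: mean(D − bx). Given x, its expectation is τ(1 − c), with c = (Σx)² / (8Σx²).
- If x is exactly balanced (c = 0), there is no attenuation, but the residuals carry 6 df while the variance is divided by 7. The true error is P(|t6| > 2.365 × √(6/7)) = 7.1%.
- Simulated mean c is 0.125 under unrestricted allocation and 0.072 under the 108 allocations. The estimate therefore averages about 0.875τ and 0.928τ.

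Attenuation vanishes under the null, where imbalance in x offsets the lost degree of freedom: unrestricted allocation gives exactly the nominal 5.0%. Restriction on x removes some of that offset.

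**Simulation.** Gaussian pair differences, at least 300,000 trials per setting. Where restriction tracks the covariate only partly or not at all, the covariate correlation is 0.5. Ranges reflect repeat runs.

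| Restriction and covariate ordering | Null error: 7 df / 6 df | Non-coverage, one-SD effect: 7 df / 6 df | Regression, 6 df (null or effect) |
|---|---|---|---|
| Same in every pair | 5.7–5.9% / 5.1–5.3% | 6.2–6.3% / 5.5–5.6% | 4.9–5.0% |
| Agree in 75% of pairs | 5.1–5.2% / 4.6% | 7.2% / 6.5% | 5.0% |
| Unrelated, or unrestricted | 5.0% / 4.4% | 7.3–7.7% / 6.5–6.9% | 5.0–5.1% |

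A binomial version of the first row with a logistic first stage (an assumed 100 or 200 HIV-positive participants per site, k_m 0.10 or 0.15, 6,000 trials per setting) gives null error of 5.2 to 5.9% on 7 df.

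**Interval width.** Critical values are 2.365 (7 df) and 2.447 (6 df), a ratio of 1.035. Dividing the residual variance by 6 as well gives 1.035 × √(7/6) = 1.118. The median two-stage interval is 0.872 to 0.896 times the regression interval, so the latter is 12 to 15% wider. Across settings and ways of averaging the range is roughly 9 to 18%.

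**Strata of 4 pairs.** The critical value is 3.182 on 3 df and 4.303 on 2 df, a ratio of 1.35.

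**The case against.** The strongest reply is that the plan is silent rather than wrong. The t-test sentence in 13.9.3 follows the unadjusted differences. The adjustment sentence comes later and refers to 13.9.1, which names a paired t-test without df, and 13.9.2 and 13.9.3 repeat the method without elaborating. A textbook is cited for the two-stage procedure (13.9.1, sensitivity analyses) and may deal with this case; it was not available here. It is true that 7 df is nowhere written. But an analyst following the text would run an ordinary paired t-test on 8 residual differences, which means 7 df, and no passage signals a departure.

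Three stronger readings are tempting, and the documents do not support them.
- *The type I error is definitely above 5%.* The null excess arises only through the restriction. Section 13.6 does not say which survey supplied its suppression and viremia values, and 13.5 says both the 2012/2013 and 2016/2017 surveys were considered for matching. Recent testing, awareness, care visits and ART use are not listed as restriction factors. For them the null error may well be nominal.
- *Using 6 df instead of 7 cures it.* Non-coverage stays at about 5.6 to 6.9%, because attenuation from ignoring arm remains.
- *The individual-level mixed models have the same fault.* Section 13.9.3 lists "random effects (e.g., clusters), scaled RDS weights as sampling weights" among sensitivity options but names no test or df method, so no error can be attributed to them.

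**Conclusion.** The point holds for the cluster-level adjusted RDS analysis. Followed as written, its 95% intervals miss a true effect of one SD of the pair differences about 6.3 to 7.7% of the time, and the null error is about 5.0 to 5.9%. The under-coverage with a true effect does not depend on how the restriction was done; the null excess does.

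The figures assume roughly normal pair differences of equal variance, a covariate correlation of about 0.5, the sign pattern used to rebuild the 108 allocations, and no explicit modelling of the RDS weights.

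The importance is low. These endpoints are exploratory, and a reader should not carry the point over to the primary cohort analysis, whose covariate is individual-level. It matters most in the 4-pair strata, where one degree of freedom is a third of what is available.

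**What to change.** In section 13.9.3, replace the two-stage paired t-test for the cluster-level adjusted RDS comparison with a pair-level regression. Regress the within-pair outcome difference (intervention minus control) on the within-pair baseline-survey difference, and report the intercept with its interval and test on 6 df (8 − 1 − 1), one fewer for each further cluster-level covariate. Intervention and baseline slope are then estimated together, which deals with both the lost degree of freedom and the attenuation; simulated error is 4.9 to 5.1% in every setting above. Apply the same rule to the other RDS outcomes adjusted for a baseline site value.

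For the PWID and MSM strata, state that the adjusted results are descriptive or that the comparison is left unadjusted, because only 2 df remain.

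The cost is two or three sentences and intervals roughly 9 to 18% wider. No new data and no change to the design or the primary analysis are needed. The change should be made before the evaluation-survey results are seen by arm.

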Protocol revisions due to COVID-19: Cohort study participant enrollment was completed in October, 2018. Study activities (follow-up visits and incentive intervention) were suspended indefinitely in March 2020. At the time research activities were suspended, all participant visit windows had closed for the 6- and 12-month follow-up visits. However, 65 and 959 participants had not completed the 18- and 24-month visits, respectively, but had not reached or were within the visit window. Because of this, in Protocol Version 2.0 we revised the primary endpoint from 24 months to 12 months. Data that was collected at 18 and 24 months will be considered in secondary and sensitivity analyses.

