13.2.1 Primary Endpoint

Survival with suppressed viral load, defined as HIV RNA <150 copies/mL in plasma or serum, at 12 months.

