13.2.2 Secondary Endpoints

- Survival with suppressed viral load at 6, 18, and 24 months.
- Proportion with at least one suppressed viral load during study follow-up (6, 12, 18, or 24 months).
- Time to ART initiation, recorded from government HIV treatment records, among cohort participants that were ART-naïve at baseline.
- Retention to HIV care during follow-up, defined as having 1 or more visits to a government ART clinic in each 6-month period of study follow-up.
- ART possession ratio (a measure of medication adherence), defined as the time in possession of ART divided by the follow-up time. Follow-up time will commence at enrollment for ART-experienced participants and at ART initiation for ART-naïve participants. Follow-up time will be censored at the end of trial follow-up, death, or loss-to-follow-up. The amount of time in possession of ART will be determined from ART dispensation logs maintained by government HIV clinics.
- Mortality, defined as a report of a participant's death from a family member or a close

friend. Death records are not maintained by local, state, or national governments in India.

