 - Current ART use, defined as the proportion of HIV-positive participants who report ART use in the prior 30 days.
 - HIV RNA suppression, defined as the proportion of HIV-positive participants with measured HIV RNA <150 copies/mL
 - Prevalence of viremic individuals in the population, defined as the proportion of all participants (HIV-negative and HIV-positive) with a measured HIV RNA ≥ 150 copies/mL
 - HIV incidence, estimated with a validated multi-assay algorithm (5) measured in HIV-seropositive participants.
- Cost-effectiveness of the incentive intervention versus control condition using the primary and secondary outcome measures, for example, the cost per additional cohort

participant with viral suppression.

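### The within-trial cost-effectiveness analysis still counts 24 months of cost against a primary outcome now measured at 12 months (exploratory analysis only)

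*Combined protocol and SAP*

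**What the plan says.** Section 13.9.3 plans two cost-effectiveness analyses. The first is within-trial: costs from the patient, payer and societal perspectives are combined "for the 24-month intervention period with the primary and secondary outcomes of the cluster-randomized trial". The second extends the trial results to a lifetime horizon by simulation. Section 13.2.3 lists as an exploratory endpoint "Cost-effectiveness of the incentive intervention versus control condition using the primary and secondary outcome measures", with no time window.

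The primary endpoint in Section 13.2.1 is survival with a suppressed viral load, "HIV RNA <150 copies/mL in plasma or serum, at 12 months". Section 13.1 gives the history: "in Protocol Version 2.0 we revised the primary endpoint from 24 months to 12 months". Section 13.2.2 lists as secondary "Survival with suppressed viral load at 6, 18, and 24 months".

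The example ratio that opens the cost-effectiveness text in 13.9.3 still uses survival with suppression at 24 months. No section sets a 12-month cost window.

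Section 13.1 also records that "Study activities (follow-up visits and incentive intervention) were suspended indefinitely in March 2020" and that at that time "65 and 959 participants had not completed the 18- and 24-month visits, respectively, but had not reached or were within the visit window".

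**The concern.** While the primary outcome stood at 24 months, the 24-month cost window matched it. Moving the outcome to 12 months without moving the window broke the match, and 13.9.3 gives no reason for wanting the two to differ. Section 13.4 also still describes the primary endpoint as a 24-month one, which suggests that the change was not carried through every section.

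The ratio is meant to be read as the cost of one additional participant surviving with suppression at 12 months. With a 24-month numerator it would include spending that took place after the effect was measured, so it could not be read that way. Policymakers, whom 13.9.3 says will be consulted, would naturally set this figure beside the trial's headline result.

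The suspension adds a second gap. Vouchers and visits stopped in March 2020, so a nominal 24-month cost window was not fully observed for many participants. The cost-effectiveness text has no rule for the missing cost months.

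**Working it through.** **Windows side by side**

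| Outcome in the ratio | Status now | Effect measured at | Cost window in 13.9.3 | Matched? |
|---|---|---|---|---|
| Survival with suppression, 12 months | Primary | 12 months | 24 months | No |
| Survival with suppression, 6 and 18 months | Secondary | 6, 18 months | 24 months | No |
| Survival with suppression, 24 months | Secondary | 24 months | 24 months | Yes |

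**Table 2 reproduced (Section 9.2).** Unit value times occasions in 24 months:

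- Pre-ART visits: 250 × 4 = 1,000
- ART initiation: 500 × 1 = 500
- Monthly refills: 150 × 24 = 3,600
- Motivational interviews: 100 × 8 = 800

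All four agree with the stated maxima (INR).

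**Voucher ceiling by window, no suspension.** Assumptions: every available voucher is earned, no pre-ART visit voucher is paid, and voucher time counts from the start of follow-up. For m months on ART the ceiling is 150 × m + 100 × (completed 3-month intervals). Add 500 for a participant who is ART-naïve and starts at once.

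| Months | On ART throughout | ART-naïve, starting at once |
|---|---|---|
| 12 | 1,800 + 400 = 2,200 | 2,700 |
| 17 | 2,550 + 500 = 3,050 | 3,550 |
| 18 | 2,700 + 600 = 3,300 | 3,800 |
| 24 | 3,600 + 800 = 4,400 | 4,900 |

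Ratio of 24 to 12 months: 4,400 / 2,200 = 2.00 and 4,900 / 2,700 = 1.81. In general the ratio is 1 + (vouchers earned after month 12) / (vouchers earned in months 1–12).

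**With the suspension.** Section 13.1 states "Cohort study participant enrollment was completed in October, 2018", so the last enrollees had about 17 months (October 2018 to March 2020). Of the 959 without a 24-month visit, 65 still had an open or future 18-month visit. The other 959 − 65 = 894 had completed that visit or passed its window. Place the 65 at 17 months, the 894 at 18 (the earliest plausible point) and everyone else at 24.

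Vouchers are paid only at intervention sites, and neither the split of the 959 between arms nor the number enrolled is stated. Two illustrations:

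- *Same share in both arms, 2,400 enrolled (the planned maximum).* On ART: (1,441 × 4,400 + 894 × 3,300 + 65 × 3,050) / (2,400 × 2,200) = 9,488,850 / 5,280,000 = 1.80. Naïve: (1,441 × 4,900 + 894 × 3,800 + 65 × 3,550) / (2,400 × 2,700) = 10,688,850 / 6,480,000 = 1.65.
- *All 959 in an intervention arm of 1,200 (extreme, but not excluded).* On ART: (241 × 4,400 + 894 × 3,300 + 65 × 3,050) / (1,200 × 2,200) = 4,208,850 / 2,640,000 = 1.59. Naïve: (241 × 4,900 + 894 × 3,800 + 65 × 3,550) / (1,200 × 2,700) = 4,808,850 / 3,240,000 = 1.48.

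If instead the 894 had nearly all reached 24 months, the even-split ratios would be 10,472,250 / 5,280,000 = 1.98 and 11,672,250 / 6,480,000 = 1.80.

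**The case against.** The strongest reply is that the plan nowhere says in so many words that 24-month cost will be divided by a 12-month effect. The only ratio with a time stamp is the 24-month example in 13.9.3. It is matched and still concerns a listed outcome. On this view the text is merely out of date, and any analyst would align the windows.

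Part of this stands: the 24-month ratio is sound as a secondary result. But it is given only as an example. Section 13.2.3 calls for a ratio on the primary outcome, and the only window that 13.9.3 offers for it is 24 months. Aligning the windows later would be an unplanned choice.

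A second reply is that missing data are already covered. Section 13.9.1 counts a missed 12-month visit as failure, and 13.9.2 says that other time points are analysed similarly. That deals with outcomes in general terms. It does not say how to treat participants whose 18- or 24-month window was open or not yet reached at the suspension, and it says nothing about costs.

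A third reply is that the voucher ratios are fragile. This is correct. They depend on the arm split, on enrolment and on when voucher time starts. Sections 8 and 13.6 place roll-out at or near the end of enrolment. If visits were timed from the baseline visit, early enrollees could have earned little in months 1–12 and the ratio could exceed 2.0. None of the suspension figures is a lower bound.

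**Conclusion.** The inconsistency is real and rests on the current text alone: as written, the primary-outcome ICER has mismatched windows, as do the ratios for suppression at 6 and 18 months. It should be corrected, but it is confined to an exploratory analysis.

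The voucher ceilings show a factor of 1.8 to 2.0 without the suspension, and less with it by an undetermined amount, under full earning and voucher time counted from the start of follow-up.

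Three stronger conclusions might be inferred, and the documents do not support them.

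- *That the ICER would be wrong by about a factor of two.* Vouchers are only one cost. Care, medication and productivity costs also enter, observed uptake is not given, and the patient out-of-pocket perspective is not described by voucher ratios at all. Neither the size nor the direction of the net effect on the full ICER can be determined.
- *That the efficacy result or the GDP-based judgement is compromised.* The efficacy analysis uses no cost data, and the GDP thresholds in 13.9.3 apply to the lifetime ICER per DALY. Whether mismatched inputs would feed the lifetime model is not stated.
- *That the whole within-trial analysis is mismatched.* The 24-month ratio is not.

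**What to change.** In Section 13.9.3:

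1. State that, for survival with viral suppression at a fixed time point, incremental costs are counted from the start of follow-up to that same time point.
2. Name the 12-month incremental cost per additional participant surviving with suppression at 12 months as the primary-outcome ICER.
3. Keep the 24-month ICER as secondary. Apply one stated treatment to both the costs and the outcomes of participants whose 18- or 24-month follow-up was cut off by the suspension.
4. Define windows separately for outcomes without a fixed time point (HIV incidence from the RDS survey, new diagnoses, time to ART initiation). The rule in item 1 does not suit them.
5. Optionally, say that the trial results carried into the lifetime model are cost and effect results with matched windows.

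The cost is a wording change and a minor re-cut of costs at 12 months. Appendix I schedules healthcare-utilization questions and ART-book abstraction at the 6- and 12-month visits, so no new data are needed. The recall period of the utilization questions is not stated and should be checked before costs are cut at 12 months.
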